## LIST OF ABBREVIATIONS

Abbreviation	Definition
6m-DB	6-month double-blind placebo-controlled
AAR	Annualized attack rate
ADP	ALA dehydratase deficient porphyria
AE	Adverse event
ALA	Aminolevulinic acid
ALAS1	Aminolevulinic acid synthase
ALP	Alkaline phosphatase
ALT	Alanine aminotransferase
ANCOVA	Analysis of covariance
AST	Aspartate aminotransferase
ATC	Anatomical Therapeutic Class
AUC	Area under curve
BMI	Body mass index
CI	Confidence interval
CSR	Clinical study report
CTCAE	Common Terminology Criteria for Adverse Events
DB	Double-blind
DMC	Data monitoring committee
ECG	Electrocardiogram
eCRF	Electronic case report form
HBMS	Hydroxymethylbilane Synthase
HCP	Hereditary Coproporphyrria
HLT	High Level Term
HRQOL	Health-related quality of life
IA	Interim analysis
ICH	International Council for Harmonisation
IRS	Interactive response system
ISR	Injection site reaction
LLN	Lower limit of normal
MedDRA	Medical Dictionary for Regulatory Activities
MI	Multiple imputation
MMRM	Mixed effect model repeated measurement

Abbreviation	Definition
mRNA	messenger RNA
NCI	National Cancer Institute
OLE	Open label extension
PBG	Porphobilinogen
PD	Pharmacodynamics
PGIC	Patient Global Impression of Change
PK	Pharmacokinetics
PMM	Pattern Mixture Model
PPS	Per Protocol Set
PT	Preferred Term
Q1	First quartile
Q3	Third quartile
SAE	Serious adverse event
SAP	Statistical analysis plan
SC	Subcutaneous
SD	Standard deviation
SEM	Standard error of mean
SMQ	Standardized MedDRA Query
SOC	System organ class
SSR	Sample size reassessment
SUSAR	Suspected Unexpected Serious Adverse Reaction
ULN	Upper Limit of Normal
VP	Variegate porphyria
WHO	World Health Organization

## 1. INTRODUCTION

Acute hepatic porphyrias (AHPs) are a family of rare, serious and life-threatening disorders characterized by acute and severe neurovisceral attacks, often requiring hospitalization or urgent healthcare visit, as well as by chronic debilitating symptoms. Patients are treated with intravenous hemin during acute attacks, but there is a high unmet need for safe and efficacious therapies to prevent attacks and decrease the chronic symptoms in between attacks. Givosiran is an investigational RNA interference (RNAi) agent in development for the treatment of AHPs in adult and adolescent patients. It acts to inhibit synthesis of liver aminolevulinic acid synthase (*ALAS1*) messenger RNA (mRNA) with consequent reductions in aminolevulinic acid (ALA) and porphobilinogen (PBG) levels, the neurotoxic intermediates that are causal in this disease. Givosiran is formulated for administration via subcutaneous (SC) injection.

The ENVISION Study (ALN-AS1-003) is a Phase 3 study designed to evaluate the efficacy and safety of SC-administered givosiran in patients with AHPs. This statistical analysis plan (SAP) outlines the methods to be used in the analysis of study data in order to address the study objectives of Study ALN-AS1-003. Any change to the data analysis methods described in the protocol, as well as the justification for the change, will be described in the SAP and clinical study report (CSR).

An original version of the SAP was signed off on Dec 05, 2017. The SAP amendment 1 provided updated plan for analysis of the data and was signed off on Sep 11, 2018, prior to the interim analysis. This SAP amendment 2 provides detailed planned analyses for data in the OLE periods and will be finalized and signed off before the final analysis of the 6-month double-blind (6m-DB) data and the unblinding of treatment assignments. The changes in these SAP amendments are documented in Section 7.

## 2. STUDY OVERVIEW

[figure not shown]
### 2.1. Synopsis of Study Design

The ENVISION Study (ALN-AS1-003) is a multicenter, multinational Phase 3 study designed to evaluate the efficacy and safety of givosiran in approximately 74 patients with AHPs; the study is comprised of a 1:1 randomized, double-blind, placebo-controlled period of 6 months, followed by an open-label extension (OLE) period of up to 30 months to evaluate the long-term safety and efficacy of givosiran.

Patients who crossed over to the OLE period prior to the implementation of the protocol amendment 3 (i.e., under amendment version 1 or 2) and are receiving a 2.5 mg/kg once monthly givosiran dose will remain on that dose. Upon entry to the OLE period under amendment version 3, patients will cross over to receive a 1.25 mg/kg once monthly dose of givosiran. Starting at Month 13 (when 6 months of open-label givosiran dosing have been completed), patients in the once monthly 1.25 mg/kg treatment group who experience inadequate disease control may have their monthly dose increased to 2.5 mg/kg, upon discussion and agreement by the Investigator and medical monitor and demonstration of tolerability to givosiran and if ALA criteria are met (urine ALA levels (mmol/mol Cr) are not stably maintained  $\leq$ ULN or are inducible).

The study design schema is presented in [Figure 1](#).

**Figure 1: Study Design**

Abbreviations: Am ≤2=original protocol (06 Sept 2017), protocol amendment 1 (04 May 2018), and protocol amendment 2.0 (26 July 2018); Am 3=protocol amendment 3 (21 Sept 2018)

## 2.2. Randomization Methodology

Patients will be randomized 1:1 to the givosiran treatment arm and the placebo arm in a double-blinded manner. Treatment will be stratified at randomization by AHP type (acute intermittent porphyria (AIP) [with genetic evidence of mutation in the hydroxymethylbilane synthase (*HMBS*) gene] vs hereditary coproporphyrria (HCP), variegate porphyria (VP), ALA dehydratase deficient porphyria (ADP), or any AHP without identified mutation in a porphyria-related gene).

Randomization for AIP patients will be further stratified by each patient’s use of hemin prophylaxis regimen at the time of screening and by each patient’s historical annualized attack rate prior to randomization. Patients on a hemin prophylaxis regimen prior to study entry will be stratified by their historical annualized attack rate: <7 attacks vs ≥7 attacks. Patients who were not on a hemin prophylaxis regimen prior to study entry will be stratified by their historical annualized attack rate: <12 attacks vs ≥12 attacks.

## 2.3. Blinding

Treatment assignments will be maintained by the Interactive Response System (IRS) which has controlled access limited to supply chain team members. Any unplanned unblinding occurring during the 6-month double-blind placebo-controlled treatment period (referred to as the 6m-DB period hereafter) will be documented and reported in the CSR.

The independent (external) data monitoring committee (DMC) and an independent (external) biostatistics group supporting the DMC will have access to subject level treatment assignments throughout the study.

An unblinded interim analysis (IA) will be conducted when approximately 40 AIP patients have completed at least 3 months of the double-blind treatment period. This IA will be based on creatinine normalized urinary ALA (referred to as ALA hereafter) data at 3 months for regulatory filing, and the analysis will be performed by the ALA IA independent statistician and programmer. The IA Filing Decision Committee at Alnylam will review data provided by the ALA IA independent statistician and programmer and decide whether to proceed to filing based on the IA results. If the committee makes an affirmative filing decision based on the IA, an Alnylam unblinded IA filing team will be formed and will have access to treatment assignment information in patients included for IA. They will not have access to post-IA patient-level study data until the 6m-DB period data are locked and unblinded, except for access to unblinded Suspected Unexpected Serious Adverse Reaction (SUSAR) safety data as shared with the agency via regular pharmacovigilance (PV) process, and safety data on the approximately 40 AIP patients included in the IA needed to prepare the 90-day safety update.

A blinded study conduct team will be in place throughout the 6m-DB period of the study regardless of the ALA interim analysis results. The blinded study conduct team will not have access to treatment assignment or any information that could reveal treatment assignment (e.g. PK, ALA, PBG, and ALAS1) until the study is unblinded for the primary efficacy analysis at Month 6.

Details about the specifics of the blinding aspects for the whole, including before, during, and after the IA are outlined in the Blinding Plan. Details about the measures taken for the unblinded IA, including concepts and plans for how the IA will be conducted and maintenance of data integrity are outlined in the Data Integrity Plan (Amendment 3, 07Sep2018).

## **2.4. Study Procedures**

The schedule of assessments is described in the study protocol (Table 1, Table 2, and Table 3).

## **3. OBJECTIVES AND ENDPOINTS**

### **3.1. Objectives**

#### **3.1.1. Primary Objective**

- Evaluate the effect of givosiran, compared to placebo, on the rate of porphyria attacks requiring hospitalization, urgent healthcare visit, or IV hemin administration at home in patients with AIP

#### **3.1.2. Secondary Objectives**

- Evaluate the effects of givosiran, compared to placebo, on urinary ALA levels in patients with AIP
- Evaluate the effects of givosiran, compared to placebo, on urinary PBG levels in patients with AIP

- Evaluate the effects of givosiran, compared to placebo, on hemin usage in patients with AIP
- Evaluate the effects of givosiran, compared to placebo, on the rate of porphyria attacks requiring hospitalization, urgent healthcare visit, or IV hemin administration at home in patients with any AHP
- Evaluate the effects of givosiran compared to placebo in patients with AIP on the symptoms of pain, nausea, and fatigue
- Evaluate the effects of givosiran, compared to placebo, in patients with AIP on the Physical Component Summary (PCS) of the 12-item Short-Form Health Survey (SF-12)
- Evaluate the safety and tolerability of givosiran in patients with any AHP

### **3.1.3. Exploratory Objectives**

- Evaluate the effects of givosiran, compared to placebo, in patients with AIP and in patients with any AHP over the 6m-DB period on:
  - Rate of all porphyria attacks (requiring hospitalization, urgent healthcare visit, IV hemin administration at home, or treated at home without IV hemin)
  - Urinary ALAS1 mRNA levels
  - Analgesic usage (opioid and non-opioid)
  - Additional quality of life (QOL) measures, including missed days of work/school
- Assess the treatment effect of givosiran at evaluated doses over the OLE period in patients with AIP and in patients with any AHP who had previously been randomized to placebo treatment
- Assess the long-term treatment effect of givosiran in patients with AIP and in patients with any AHP
- Characterize the PK of and assess the antidrug antibodies (ADA) of givosiran in patients with any AHP

## **3.2. Endpoints**

### **3.2.1. Primary Endpoint**

Annualized rate of porphyria attacks requiring hospitalization, urgent healthcare visit, or IV hemin administration at home in patients with AIP over the 6m-DB period.

### **3.2.2. Secondary Endpoints**

- Urinary ALA levels in patients with AIP at 3 months
- Urinary ALA levels in patients with AIP at 6 months
- Urinary PBG levels in patients with AIP at 6 months

- Annualized rate of administered hemin doses (evaluated by annualized days of hemin use, see Section 6.5.2 for details) in patients with AIP over the 6m-DB period
- Annualized rate of porphyria attacks requiring hospitalization, urgent healthcare visit, or IV hemin administration at home in patients with any AHP over the 6m-DB period
- Daily worst pain score as measured by Brief Pain Inventory-Short Form (BPI-SF) numeric rating scale (NRS) in patients with AIP over the 6m-DB period
- Daily worst fatigue score as measured by Brief Fatigue Inventory-Short Form (BFI-SF) NRS in patients with AIP over the 6m-DB period
- Daily worst nausea score as measured by NRS in patients with AIP over the 6m-DB period
- Change from baseline in the Physical Component Summary (PCS) of the 12-item Short-Form Health Survey (SF-12) in patients with AIP at 6 months

### 3.2.3. Exploratory Endpoints

Exploratory endpoints will be measured in patients with AIP and in patients with any AHP over the 6m-DB period or over the OLE period:

- Rate of porphyria attacks requiring hospitalization, urgent healthcare visit, or IV hemin administration at home
- Rate of all porphyria attacks
- Rate of administered hemin doses (evaluated by annualized days of hemin use, see Section 6.5.2 for details)
- Urinary ALA and PBG levels
- Urinary ALAS1 mRNA levels
- Daily worst pain, daily worst fatigue, and daily worst nausea scores over 12 months
- PCS of the SF-12
- EQ-5D-5L index score
- Patient Global Impression of Change (PGIC)
- Porphyria Patient Experience Questionnaire (PPEQ)
- Analgesic usage (opioid and non-opioid)
- Plasma PK parameters of givosiran
- Incidence and titer of ADAs

### 3.2.4. Safety Endpoints

The primary safety parameter is the adverse events (AEs) that occurred on or after the time of the first dose of study drug is administered. Safety parameters also include vital signs, ECGs, clinical laboratory assessments, and physical exams. The primary summaries of the safety of givosiran versus placebo will be based on safety parameters assessed during the 6m-DB period. The

frequency of AEs will also be evaluated over the entire study including the 6m-DB and OLE periods. Since porphyria attacks will be recorded for efficacy assessment of the study drug, they will not be treated as AEs or SAEs.

#### 4. PATIENT POPULATION

The populations (analysis sets) are defined as follows:

- Full Analysis Set (FAS): All randomized patients who received at least one dose of study drug. Patients will be grouped by their randomly assigned treatment group (i.e. as randomized).
- AIP patients in the Full Analysis Set (FASAIP): All randomized AIP patients (with identified mutation in the *HMBS* gene) who received at least one dose of study drug. Patients will be grouped by their randomly assigned treatment group (i.e. as randomized).
- Per Protocol Analysis Set (PPS): All randomized AIP patients (with identified mutation in the *HMBS* gene) who received at least 4 doses (>60%) of study drug during the 6-month double-blind period, were followed for collection of attack data through 6 months ( $\geq 162$  days) and did not experience major protocol deviations that may impact the primary efficacy results (e.g., not meeting the key inclusion/exclusion criteria). Patients will be analyzed according to their randomly assigned treatment group.
- Safety Analysis Set (SAS): All patients who received at least one dose of study drug, grouped according to the treatment actually received.
- PK Analysis Set: All patients who received at least one dose of study drug and have evaluable PK data contributing to the estimation of PK parameter.
- PD Analysis Set: All patients who received at least one dose of study drug and who have baseline and at least one post-dose urine sample for the determination of ALA or PBG.
- All Givosiran Treated Set: All patients who received at least one dose of givosiran, including patients who took givosiran during the 6m-DB period and patients who first took placebo during the 6m-DB period and switched to givosiran during the OLE period.

Both FAS and FASAIP will be used to evaluate efficacy endpoints. The primary endpoint will also be analyzed using the Per Protocol Set. Safety during the 6m-DB period will be analyzed using the Safety Analysis Set. The PK and PD Analysis Sets will be used to conduct PK and PD analyses, respectively. The All Givosiran Treated Set will be used to summarize long-term efficacy and safety data during givosiran treatment. See Section 5.10 for details. Number of patients included in all analysis sets will be provided.

## 5. GENERAL STATISTICAL METHODS

### 5.1. Determination of Sample Size

The planned total enrollment for the study is approximately 74 patients, including approximately 70 AIP patients.

Seventy patients will yield at least 90% power to detect a 45% reduction in the annualized attack rate at a 2-sided 5% significance level assuming a mean annualized attack rate of 8, a standard deviation (SD) of 5 in the placebo arm (mean/SD of 4/2.9 for 6 months to preserve the over-dispersion of 3.8), and a mean annualized attack rate of 4.4 with SD of 3 in the givosiran arm (mean/SD of 2.2/1.8 for 6 months to preserve the over-dispersion of 4.2), using a negative binomial model. This study design will still have at least 80% power even if the dropout rate is as high as 15% under the same assumptions.

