8.1. Determination of Sample Size

The planned total enrollment for the study is approximately 74 patients, including approximately 70 AIP patients.

In this study, 70 patients will have at least 90% power to detect a 45% reduction in the annualized attack rate at a 2-sided 5% significance level assuming a mean annualized attack rate of 8, a standard deviation (SD) of 5 in the control arm, and a mean annualized attack rate of 4.4 with SD

of 3 in the givosiran arm, using a negative binomial model. This study design will still have at least 80% power even if the dropout rate is as high as 15% under the same assumptions.

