## 5.7. Multiple Comparisons/Multiplicity

At the time of the unblinded interim analysis, only the first secondary efficacy endpoint ALA levels at Month 3 will be assessed. A significance level of 0.001 will be used when comparing the ALA levels between the two treatment arms using an ANCOVA model.

For the final analyses of the 6m-DB primary treatment period, a significance level of 0.049 will be used to test the efficacy endpoints, reflecting a penalty of 0.001 for the unblinded interim analysis. A fixed-sequence testing strategy for the primary and secondary endpoints will be implemented to control the overall type I error rate. The primary endpoint will be compared between treatment arms at the significance level of 0.049. If the test is statistically significant, then the secondary endpoints will each be tested at the same significance level of 0.049 in the order specified in the efficacy endpoint section (Section 3.2 ). If the test of an endpoint in the sequence is not statistically significant, the testing of remaining endpoints in the sequence will stop and the null hypotheses for the subsequent tests will not be rejected.

There will be no multiplicity adjustment for exploratory endpoints.

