### 6.5.1. Primary Endpoint

The primary endpoint of the study is the annualized rate of porphyria attacks requiring hospitalization, urgent healthcare visit, or IV hemin administration at home in patients with AIP over the initial 6m-DB period. The primary analysis set for the primary endpoint is  $FAS_{AIP}$  (defined in Section 4).

The number of qualifying porphyria attacks is annualized for each patient using below formula:

$$\text{Annualized attack rate (AAR)} = \frac{\text{total number of porphyria attacks}}{\text{total number of days in the treatment period}} \times 365.25.$$

Let  $\lambda_G$  represent the mean AAR for givosiran arm and  $\lambda_O$  represent the mean AAR for the placebo arm. The hypotheses of the primary analysis are:

$$H_0: \frac{\lambda_G}{\lambda_O} = 1 \quad H_A: \frac{\lambda_G}{\lambda_O} \neq 1$$

The statistical significance level for the primary analysis of the primary endpoint is 2-sided 0.049. An estimated AAR ratio :  $\frac{\lambda_G}{\lambda_O} < 1$  and 2-sided p-value  $< 0.049$  will lead to rejection of  $H_0$ .

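### The stated power of at least 90% with 70 AIP patients assumes half a year and alpha 0.05; at the scheduled 168 days and alpha 0.049 it is about 88–89%

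*SAP*

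**What the plan says.** **Power statement.** SAP 5.1: "Seventy patients will yield at least 90% power to detect a 45% reduction in the annualized attack rate at a 2-sided 5% significance level". Protocol 8.1: "70 patients will have at least 90% power to detect a 45% reduction". The Statistical Methods part of the synopsis gives the same figure. The assumed annual mean/SD are 8/5 on placebo and 4.4/3 on givosiran. For placebo, SAP 5.1 converts these to "mean/SD of 4/2.9 for 6 months to preserve the over-dispersion of 3.8"; for givosiran it uses 2.2/1.8. Both six-month means are exactly half the annual means. The same paragraph claims at least 80% power if dropout reaches 15%.

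**Alpha of the test.** SAP 5.7: "a significance level of 0.049 will be used to test the efficacy endpoints", because 0.001 is set aside for the interim analysis. SAP 6.5.1: "The statistical significance level for the primary analysis of the primary endpoint is 2-sided 0.049".

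**Length of follow-up.** Protocol Table 1 puts the Month 6 visit at Day 169 with a window of 7 days either way, and the first open-label dose is given at that visit (Table 1, footnote m). SAP 5.10 ends the double-blind period at that dose. SAP 6.5.1.4 takes Day 162 as the earliest expected end. The primary model (SAP 6.5.1.1) uses each patient's own time in the period as the offset.

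**Allocation and enrollment.** SAP 2.2: "Patients will be randomized 1:1 to the givosiran treatment arm and the placebo arm". SAP 7.1 reports that the sample size reassessment was not carried out because more patients than expected had been randomized. It does not say how many.

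**The concern.** The power section was not brought into line with two things fixed elsewhere in the plan. Six 28-day cycles are 168 days, or 0.46 year. Expected counts per patient are therefore about 8% below those assumed (168/182.6 = 0.92), and fewer events mean less information on the rate ratio. The primary test also uses a slightly smaller alpha than the power statement.

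A floor of at least 90% is a stated property of the primary test. As shown below, the SAP's own inputs put power at about 90% with little or no margin, so even a small loss can take it below the floor. No power formula or software is named, so a reader cannot tell whether the statement survives.

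**Working it through.** **Inputs.** 35 patients per arm (70, allocated 1:1). Annual rates 8 and 4.4, so the rate ratio is 0.55 and |ln 0.55| = 0.5978. Negative binomial dispersion k = (SD² − mean)/mean²:

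- placebo: (25 − 8)/64 = 0.2656, and 1/k = 3.76
- givosiran: (9 − 4.4)/19.36 = 0.2376, and 1/k = 4.21

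These match the SAP's 3.8 and 4.2. The six-month SDs follow as √(4 + 16 × 0.2656) = 2.87 and √(2.2 + 4.84 × 0.2376) = 1.83, which round to the SAP's 2.9 and 1.8. The SAP therefore used t = 0.5 year.

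**Formula (Wald, log rate ratio).** SE² = [1/(8t) + 0.2656 + 1/(4.4t) + 0.2376]/35, and power = Φ(0.5978/SE − z).

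**Step 1: the plan's own figure (t = 0.5, alpha 0.05).** SE² = (0.2500 + 0.2656 + 0.4545 + 0.2376)/35 = 0.0345, SE = 0.1858. 0.5978/0.1858 = 3.218; minus 1.960 is 1.258; power 89.6%. Other methods give 89.9% to 92.0% (table), so the stated figure reproduces to rounding.

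**Step 2: the scheduled design (t = 168/365.25 = 0.460, alpha 0.049).** Expected counts are 3.680 and 2.024. SE² = (0.2717 + 0.2656 + 0.4941 + 0.2376)/35 = 0.0363, SE = 0.1904. 0.5978/0.1904 = 3.140; minus 1.969 is 1.171; power 87.9%.

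**Step 3: other methods, 35 per arm.** The simulations fit an unadjusted negative binomial model with common dispersion to 20,000 trials per setting (Monte Carlo SE about 0.2 point).

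| Method | 0.5 year, 0.05 | 168 days, 0.049 | Loss (points) |
|---|---|---|---|
| Wald formula | 89.6% | 87.9% | 1.7 |
| Wald, SAP's rounded SDs | 89.9% | 88.2% | 1.7 |
| Null variance from pooled rate | 90.4% | 88.9% | 1.5 |
| Null variance from placebo (reference) rate | 92.0% | 90.8% | 1.2 |
| Simulation, Wald test | 90.3% | 88.6% | 1.7 |
| Simulation, likelihood ratio test | 89.9% | 88.2% | 1.7 |

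Repeat simulations of the second setting lay between 87.9% and 88.9%.

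**Step 4: split of the loss (Wald).** Alpha 0.049 alone: 89.4%. 168 days alone: 88.1%. Follow-up costs about 1.5 points and alpha about 0.2.

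**Step 5: sensitivity to the period (Wald, 0.049).** 162 days: 87.2%. 175 days: 88.7%.

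**Step 6: dropout.** With 35 × 0.85 = 29.75 per arm, and dropouts contributing nothing, Wald power at 168 days and 0.049 is 82.3%.

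**Step 7: number for 90% (Wald, 168 days, 0.049).** 74 AIP patients give 89.6%; 76 give 90.4%.

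**The case against.** - **The SAP's figure is right on its own inputs.** This stands. The methods in the table give 89.6% to 92.0% there, so SAP 5.1 contains no arithmetic mistake. The fault lies in the inputs, which do not match the schedule or the test.
- **The result depends on the formula.** This stands in part. With the null variance taken from the placebo rate, the claim survives both corrections at about 91%. But that is a planning approximation, and simulation of an unadjusted version of the planned model stays below 90%.
- **168 days is inferred.** True: no section states it as the analysis period. The visit window and the rule that delays the open-label dose after hemin use will lengthen follow-up for some patients. By the Wald formula, 175 days still gives only 88.7%.
- **The loss is small compared with the uncertainty in the assumed rates and SDs.** This also stands, and it is why the point is minor.

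A reader might infer that the trial was underpowered, or that dropping the sample size reassessment removed a needed safeguard. The documents do not support either reading. The reassessment was optional and concerned blinded attack rates, not follow-up time or alpha. The reason given for dropping it, enrollment above plan, raises power. A reader might also give the alpha reduction equal weight with follow-up; it accounts for only about 0.2 point.

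**Conclusion.** The mismatch is real and its effect small. For 70 AIP patients over the scheduled 168 days at two-sided 0.049, an unadjusted negative binomial test has about 88–89% power, which is 1 to 2 points under the stated floor. The 80% statement at 15% dropout holds.

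This rests on the plan's assumed rates and SDs, equal arms of 35, a common follow-up of 168 days derived from the visit schedule, and no gain from covariates. The planned model adjusts for prior hemin prophylaxis and historical attack rate, which could raise power, but the documents give no figures from which to estimate the gain. The number of AIP patients randomized is not given either, so the power of the trial as enrolled could be above 90%. The finding corrects a stated figure and is not evidence that the trial is too small.

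**What to change.** In SAP 5.1, Protocol 8.1 and the synopsis:

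1. Restate the power as about 88–89% for 70 AIP patients over the scheduled 168 days at two-sided 0.049.
2. Name the power method (formula or simulation, and the null variance used), since that choice decides which side of 90% the figure falls on.
3. Add the power for the number of AIP patients actually randomized. About 76 restores 90% by the Wald formula.
4. If a gain from the stratification covariates is relied on, show the calculation and its assumptions.

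The cost is a few lines of text and a slightly less favourable planning figure. No patients, procedures, tests or alpha levels change.
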